#### 4.3.1 Array Inserter for the NeuroPort Array

The Array Inserter is manufactured by Blackrock Microsystems, Salt Lake City, UT, USA.

The array inserter allows for the rapid insertion of a surface aligned array into cerebral cortex. Key features include: a multiple-use trigger-actuated pneumatic piston, and a pressure source. Piston stroke length can be adjusted, which prevents excessive dimpling of cortical tissues upon insertion. Piston actuation is achieved through an actuated chamber that is pressurized with a 120 VAC driven pump. The power source is patient isolated with a hospital grade isolation transformer. This inserter is part of the 510(k) cleared device, the NeuroPort Array.

#### 4.3.2 NeuroPort Biopotential Signal Processor

The NeuroPort Biopotential Signal Processor is manufactured by Blackrock Microsystems, Salt Lake City, UT, USA.

Neural signals read out by the passive implant device are recorded via the NeuroPort Biopotential Signal Processor. The NeuroPort Biopotential Signal Processor allows for the recording of up to 128 channels of activity. Key features include: an optically isolated amplifier capable of recording 128 channels at 30 kHz with 16-bit resolution.

The power source is 120 VAC through a hospital grade isolation transformer. The NeuroPort Biopotential Signal Processor complies with the relevant safety standards for intra-operative and hospital monitoring settings: IEC 60601-2-26, IEC 60601-1-2, UL 2601-1, CAN/CSA-C22.2 no. 601.1-M90.

The NeuroPort Biopotential Signal Processor has received 510(k) clearance for use. It will not be modified in any way from its original 510(k) clearance for use.

5.0 Selection and Withdrawal of Subjects

## 5.1 Inclusion Criteria

Table 5-1 outlines the inclusion criteria which will be applied to study applicants, as well as the method of evaluating each criterion and the threshold for each criterion. The methods used to evaluate inclusion criteria consist of verbal discussion, medical record review, and consultation with the subject's primary care physician.

Table 5-1. Inclusion criteria, methods of evaluation, and thresholds for inclusion.

Criterion	Method of Evaluation	Threshold
High cervical spinal lesion	Medical Records	History of spinal lesion (C4 and above), with 0/5 distal arm muscle strength in both arms: C5 – Deltoid and biceps C6 – Wrist extensors C7 – Triceps C8 – Finger flexors T1 – Finger abductors  Occurred at least one year prior to enrollment  Stable for three months prior to enrollment (no signs of improvement)
Age	Medical Records	18-65 years
Provide informed consent	Consultation with Physician	Must be willing and able
Understand and comply with instructions in English	Consultation with Physician	Must be able
Communicate via speech	Consultation with Physician	Must be able
Surgical clearance	Consultation with Physician	Must be cleared
Life expectancy	Consultation with Physician	Greater than 12 months
Travel up to 60 miles to study locations up to five days per week for the duration of the study	Verbal discussion	Must be willing and able
Caregiver monitor for surgical site complications and behavioral changes on a daily basis	Verbal discussion	Caregiver must be willing and able
Psychosocial support system	Verbal discussion	Must be present and stable

## 5.2 Exclusion Criteria

Table 5-2 outlines the exclusion criteria which will be applied to study subjects, as well as the method of evaluating each criterion and the threshold for each criterion. The methods used to evaluate exclusion criteria consist of some tests (as specified in Table 5-2), survey (i.e., verbal and written interaction with patient), medical record review, consultation with the subject's primary care physician, and physical examination.

Table 5-2. Exclusion criteria, methods of evaluation, and thresholds for exclusion.

Criterion	Method of Evaluation	Threshold
Presence of memory problems	Rey Auditory Verbal Learning Test	Age-dependent (Appendix, section 18.5)
Intellectual impairment	Cognitive Abilities Screening Instrument (CASI)	Score of 26 or less
Psychotic illness or chronic psychiatric disorder, including major depression if untreated	Symptom Checklist-90-Revised Test	diagnosis of Axis I or Axis II
Poor visual acuity	Snellen chart	20/30 or lower
Pregnancy	Urine Pregnancy Test	Positive (Pregnant)

Active infection or unexplained fever	Physical Examination	Evidence of either
Scalp lesions or skin breakdown	Physical Examination	Evidence of either
HIV or AIDS infection	Medical Records, blood work	Positive (infected)
Active cancer or chemotherapy	Medical Records	History of cancer in past 12 months, or evidence of need for chemotherapy during study
Diabetes	Medical Records, blood work	Any
Autonomic dysreflexia	Medical Records	History in past 3 months
History of seizure	Medical Records	Any
Implanted hydrocephalus shunt	Medical Records	Any
Previous neurosurgical history affecting parietal lobe function	Medical Records	Any
Medical conditions contraindicating surgery and chronic implantation of a medical device	Medical Records	osteomyelitis, diabetes, hepatitis, any autoimmune disease/disorder, epilepsy or history of seizures of any kind, skin disorders causing excessive skin sloughing or poor wound healing, blood or cardiac disorder requiring chronic anti-coagulation
Prior cranioplasty	Medical Records	Any
Unable to undergo MRI or anticipated need for MRI during study	Medical Records, Consultation with Physician	Any
Nursing an infant or unwilling to bottle-feed infant	Medical Records, Survey	Any
Chronic oral or intravenous use of steroids or immunosuppressive therapy	Medical Records, Survey	Any
Suicidal ideation	Medical Records, Survey	History in past 12 months
Drug or alcohol dependence	Survey	History in past 12 months
Planning to become pregnant, or unwilling to use adequate birth control	Survey	Any plan for pregnancy, or unwilling to use birth control

### 5.3 Withdrawal Criteria

Withdrawal is premature conclusion, which may occur at any time. Withdrawal is discouraged, but is a right of the subject. If the subject withdraws, he or she cannot continue to use the NPS. The clinical team and sponsor-investigator will determine whether to explant the device based on clinical and ethical considerations and the nature of the withdrawal. If the subject withdraws and has all devices explanted, there is no need for further physician monitoring of the device, and the patient will receive the standard clinical follow-up care (follow-up visits at one week, six weeks, and three months post-surgery).

The withdrawal criteria are:

- Patient request
- Attending physician (neurosurgeon, neurologist) request
- Serious infection around the percutaneous connector
- 53 weeks of implantation, unless patient opts to retain device
- Pregnancy
- Onset of epilepsy
- Significant change in neurological exam
- Development of serious adverse events, physical or psychological, including negative behavioral symptoms, major depression, or suicidal ideation
- Intracranial infection unresponsive to antibiotic treatment
- Development of intracranial hematoma requiring evacuation
- Need for urgent MRI of any kind (brain or body)

## 6.0 Stratification/Descriptive Factors/Randomization Scheme

Because this study is structured to evaluate the feasibility of the NPS, there are no elements of stratification or randomization involved in subject selection or device administration. Subjects will be selected who display symptoms characteristic of high (C4) spinal lesion. Each of these subjects will receive the same device, and will participate in the same tasks to evaluate the effectiveness of the device. The health of each subject, including the area around the implant, will be evaluated in the same way for both subjects.

## 7.0 Study Agent Administration or Intervention and Toxicity Management Plan

### 7.1 Device Administration

Each subject in this study will receive the same device. The device consists of two NeuroPort Arrays implanted in the posterior parietal cortex. One array will be implanted in Brodmann's area 5, and the second array will be implanted in the anterior intraparietal area. Each subject will undergo the same evaluations to monitor the safety of the implanted device. Each subject will participate in the same set of tasks designed to evaluate the effectiveness of the device.

### 7.2 Intervention Plan

There are no alternative therapies available for this device, and the condition which predicates this device (paralysis) is not acutely life-threatening, so a slow treatment or absence of treatment does not constitute undue risk to the subject requiring intervention. However, the presence of the device does present increased risk to the subject, particularly in terms of the risk of infection. Thus, it may be determined by the study sponsor that the device cannot be made to work without significant surgical revision or other risk-laden procedure; and, if it is so determined, the study sponsor and co-investigators may opt at their discretion to withdraw the subject from the study as a means of intervention to cease ongoing study-related risk.

### 7.3 Toxicity Mangement Plan

The NeuroPort Arrays are approved by the FDA to be in prolonged contact with CSF, bone/blood and tissue, i.e., for 30 days or less. (For the purposes of this study, an investigational device exemption has been obtained which approves permanent contact with CSF, bone/blood and tissue). Additionally, the NeuroPort Arrays are constructed using materials with a history of biocompatibility, such as titanium. In order to obtain 510(k) approval for prolonged contact, the NeuroPort Array was required to undergo a suite of tests determining its biocompatibility; the device was determined to be biocompatible for its originally intended use. Furthermore, an extensive body of literature reviewing the CerePort Array in animals and, and a smaller body of work reviewing results of the BrainGate clinical study sequence, have collectively demonstrated no chronic toxicity (see Section 1.3.1 for a review of this evidence). The sponsor and investigators of this study take the evidence at hand to support the view that the device is not toxic. Therefore, this study does not include any toxicity management strategies.

## 8.0 Assessment of Effectiveness and Safety

### 8.1 Side Effects Monitoring

#### 8.1.1 Side Effects Monitored During Study

The primary long-term risk associated with the NPS is that of infection. Infection could develop around the percutaneous connectors, or it could develop intracranially. Thus, study subjects will be monitored throughout the study to watch for signs and symptoms of both superficial and intracranial infection.

Monitoring for superficial infection will include participation of the subjects' caregivers as well as study physicians. The caregivers will be trained to observe and maintain the wound site on a daily basis. Physicians will check the wound site monthly over the course of the study.

Monitoring for intracranial infection will also include participation of the subjects' caregivers as well as study physicians. Caregivers will be trained to watch for signs of intracranial infection such as functional deficits and seizure. Physicians will conduct thorough examinations of study subjects, including both physical and neurological, on a monthly basis throughout the study.

#### 8.1.2 Side Effects Monitored After Study

As is routine for patients who undergo brain surgery, the patient will be seen for follow-up visits at one week, six weeks, and three months following the explant surgery. At these visits, the attending physician will execute a full physical and neurological examination to test for any adverse events or effects which may have occurred.

### 8.2 Adverse Event Reporting

#### 8.2.1 Adverse Event Definitions

*Adverse event.* Any untoward medical occurrence in a clinical study of an investigational device; regardless of the causal relationship of the problem with the device or, if applicable, other study treatment or diagnostic product(s).

*Associated with the investigational device or, if applicable, other study treatment or diagnostic product(s).* There is a reasonable possibility that the adverse event may have been caused by the investigational device or, if applicable, the other study treatment or diagnostic product(s).

*Disability.* A substantial disruption of a person's ability to conduct normal life functions.

*Life-threatening adverse event.* Any adverse event that places the subject, in the view of the sponsor-investigator, at immediate risk of death from the event as it occurred (i.e., does not include an adverse event that, had it actually occurred in a more severe form, might have caused death).

*Serious adverse event.* Any adverse event that results in any of the following outcomes: death, a life-threatening adverse effect, inpatient hospitalization or prolongation of existing hospitalization, a persistent or significant disability/incapacity, or a congenital anomaly/birth defect.

- *Hospitalization* shall include any initial admission (even if less than 24 hours) to a healthcare facility as a result of a precipitating clinical adverse event; to include transfer within the hospital to an intensive care unit. Hospitalization or prolongation of hospitalization in the absence of a precipitating, clinical adverse event (e.g., for a preexisting condition not associated with a new adverse event or with a worsening of the preexisting condition; admission for a protocol-specified procedure) is not, in itself, a serious adverse effect.

*Unexpected adverse event.* Any adverse event, the frequency, specificity or severity of which is not consistent with the risk information described in the clinical study protocol(s), as amended.

*Unanticipated adverse device event.* Any serious adverse event on health or safety or any life-threatening problem or death caused by, or associated with, a device, if that event, problem, or death was not previously identified in nature, severity, or degree of incidence in the investigational plan (including a supplementary plan or application),

or any other unanticipated serious problem associated with a device that relates to the rights, safety, or welfare of subjects.

#### 8.2.2 Eliciting Adverse Event Information

Clinical study subjects will be routinely questioned about adverse events at study visits.

#### 8.2.3 Recording and Assessing Adverse Events

All observed or volunteered adverse events (serious or mild) and abnormal test findings, regardless of treatment group, if applicable, or suspected causal relationship to the investigational device or, if applicable, other study treatment or diagnostic procedure(s) will be recorded in the subjects' case histories. For all adverse events, sufficient information will be pursued and/or obtained so as to permit 1) an adequate determination of the outcome of the event (i.e., whether the event should be classified as a serious adverse event) and; 2) an assessment of the causal or potential causal relationship between the adverse event and the investigational device or, if applicable, the other study treatment or diagnostic product(s).

Adverse events or abnormal test findings felt to be associated or possibly associated with the investigational device will be classified as serious or mild and will be followed until resolved or stabilized at a level acceptable to the sponsor-investigator.

#### 8.2.4 Abnormal Test Findings

An abnormal test finding will be classified as an adverse event if one or more of the following criteria are met:

- The test finding is accompanied by clinical symptoms.
- The test finding necessitates additional diagnostic evaluation(s) or medical/surgical intervention; including significant additional concomitant drug or other therapy. (Note: simply repeating a test finding, in the absence of any of the other listed criteria, does not constitute an adverse event.)
- The test finding leads to a change in study dosing or exposure or discontinuation of subject participation in the clinical study.
- The test finding is considered an adverse event by the sponsor-investigator.

#### 8.2.5 Causality and Severity Assessment

The sponsor-investigator will promptly review documented adverse events and abnormal test findings to determine 1) if the abnormal test finding should be classified as an adverse event; 2) if there is a reasonable possibility that the adverse event was caused by the investigational device or, if applicable, other study treatment or diagnostic procedure(s); and 3) if the adverse event meets the criteria for a *serious adverse event*.

If the sponsor-investigator's final determination of causality is "unknown and of questionable relationship to the investigational device or, if applicable, other study treatment or diagnostic procedure(s) are deemed necessary", the adverse event will be classified as *associated or possibly associated with the use of the investigational device or study treatment or diagnostic drug procedure(s)* for reporting purposes. If the sponsor-investigator's final determination of causality is "unknown but not related to the investigational device or, if applicable, other study treatment or diagnostic procedure(s)", this determination and the rationale for the determination will be documented in the respective subject's case history.

#### 8.2.6 Reporting of Adverse Events to the FDA

The sponsor-investigator will submit a completed FDA Form 3500A to the FDA's Center for Devices and Radiological Health for any observed or volunteered adverse event that is determined to be an unanticipated adverse device event. A copy of this completed form will be provided to all participating sub-investigators.

The completed FDA Form 3500A will be submitted to the FDA as soon as possible and, in no event, later than 10 working days after the sponsor-investigator first receives notice of the adverse event.

If the results of the sponsor-investigator's follow-up evaluation show that an adverse event that was initially determined to not constitute an unanticipated adverse device event does, in fact, meet the requirements for

reporting; the sponsor-investigator will submit a completed FDA Form 3500A as soon as possible, but in no event later than 10 working days, after the determination was made.

For each submitted FDA Form 3500A, the sponsor-investigator will identify all previously submitted reports that addressed a similar adverse event experience and will provide an analysis of the significance of the newly reported adverse event in light of the previous, similar report(s).

Subsequent to the initial submission of a completed FDA Form 3500A, the sponsor-investigator will submit additional information concerning the reported adverse event as requested by the FDA.

#### **8.2.7 Reporting of Adverse Events to the Responsible IRB**

In accordance with applicable policies of the reviewing Institutional Review Boards (IRBs), the sponsor-investigator will report, to all associated IRBs, any observed or volunteered adverse event that is determined to meet all of the following criteria: 1) *associated with the investigational device or, if applicable, other study treatment or diagnostic product(s)*; 2) a *serious adverse event*; and 3) an *unexpected adverse event*. Adverse event reports will be submitted to the IRB in accordance with the respective IRB procedures.

Applicable adverse events will be reported to the IRB as soon as possible and, in no event, later than 10 calendar days following the sponsor-investigator's receipt of the respective information. Adverse events which are 1) *associated with the investigational device or, if applicable, other study treatment or diagnostic product(s)*; 2) *fatal or life-threatening*; and 3) *unexpected* will be reported to the IRB within 24 hours of the sponsor-investigator's receipt of the respective information.

Follow-up information to reported adverse events will be submitted to the IRB as soon as the relevant information is available. If the results of the sponsor-investigator's follow-up investigation show that an adverse event that was initially determined to not require reporting to the IRB does, in fact, meet the requirements for reporting, the sponsor-investigator will report the adverse event to the IRB as soon as possible, but in no event later than 10 calendar days, after the determination was made.

#### **8.2.8 List of Adverse Events**

The following list comprises adverse events which could occur.

##### **8.2.8.1 *CNS: Infection/Vascular/CSF***

- CNS hematoma (e.g., subdural, epidural)
- CSF Leakage
- Deep Vein Thrombosis (DVT)
- Encephalitis
- Hemorrhage
- Intracranial hemorrhage
- Meningitis
- Stroke

##### **8.2.8.2 *Wound (surgery-related)***

- Bleeding
- Drainage
- Edema
- Infection (superficial)
- Irritation
- Soreness
- Pain

##### **8.2.8.3 *Pain***

- Acute, deep
- Acute, superficial
- Chronic, deep
- Chronic, superficial

- Headache

#### *8.2.8.4 Seizure*

- New seizure
- Onset of epilepsy
- Status epilepticus

#### *8.2.8.5 Cognitive Memory*

- Attention/concentration difficulty
- Confusion
- Memory difficulty
- Psychomotor slowing/encephalopathy

#### *8.2.8.6 Mood/Psychological*

- Agitation/irritability
- Anxiety/nervousness
- Depression
- Emotional lability
- Personality change
- Psychosis

#### *8.2.8.7 Language*

- Dysarthria
- Aphasia (e.g., Dysnomia, Dysphasia)

#### *8.2.8.8 Movement/Coordination*

- Ataxia
- Coordination difficulties
- Dyskinesia/Dystonia
- Involuntary movements (e.g., twitching, myoclonus, chorea)
- Tremor
- Weakness (paresis)

#### *8.2.8.9 Sensory*

- Loss of sensation (e.g., numbness, loss of proprioceptive/vibratory sensation)
- Loss of sight
- Vertigo/dizziness

#### *8.2.8.10 Coma/Death*

- Coma
- Death

#### *8.2.8.11 Allergy/Immunologic*

- Allergic reaction (e.g., wound care cleaning solution)
- Rejection (e.g., sensor or percutaneous connector)

#### *8.2.8.12 Constitutional/Systemic*

- Appetite change
- Edema
- Fatigue
- Fever
- Flu
- Hematologic
- Insomnia/other sleep disorders
- Night sweats
- Weight change

*8.2.8.13 Tumor/Cancer*

- Cancer, malignant
- Mass/lesion, benign

**8.2.9 Withdrawal of Subjects Due to Adverse Events**

An adverse event may be serious in nature and require the subject to withdraw from the study. The severity of the adverse event, and whether it constitutes a reason for withdrawal from the study, will be determined by the clinical team and sponsor-investigator. Unless otherwise indicated by the clinical team and sponsor-investigator, the device will be explanted before the subject is withdrawn from the study.

**8.3 Data Monitoring Committee**

Aptiv Solutions, Inc. (Aptiv) will perform data monitoring over the course of the study.

9.0 Clinical and Laboratory Evaluations and Clinical Calendar

See Appendix, Section 18.1.

10.0 Criteria for Evaluation and Endpoint Definitions

The objectives of this study are to evaluate the safety and effectiveness of the NPS. Each of these objectives will be measured quantitatively as defined in Table 10-1 and described in this section.

Table 10-1. Safety and Effectiveness Endpoints

Objective	Hypothesis	Method of Evaluation	Time of Assessment	Comparisons Made
To evaluate the safety of the NPS implant	Primary endpoint – implantation will not be associated with infection or irritation	Inspection of subject's scalp for evidence of reddening or discharge; review of new symptoms including possible fever, headache, visual or auditory changes, or change in mood or behavior; serial neurologic exams	Immediately after implantation and weekly thereafter	The condition of the area will be compared with its condition on previous visits  History will be obtained regarding new symptoms  Neurologic exam will be compared to baseline neuro exam
	Secondary endpoint – the Severe Adverse Event (SAE) rate will not rise above 1% for any study subjects.	The SAE rate will be calculated as the number of SAEs per implant-days.	The SAE rate will be available on a daily basis throughout the study.	The SAE rate will be continuously compared to the 1% threshold level.
To evaluate the effectiveness of the NPS	Primary endpoint – patient control over the end effector (virtual or physical), as measured by accuracy, will be significantly greater than chance when using the NPS	Calculated by the NPS computer apparatus	At the end of every study session	Assessments will be compared with chance
	Secondary endpoint – Action Research Arm Test (ARAT) scores will improve over the course of the trial when controlling the virtual or physical robotic arm	ARAT administered by occupational therapists	At 10-week intervals starting at week 3.	Scores will be compared to the baseline, i.e., the first score from week 3.
	Tertiary endpoint – using the NPS with either a virtual or physical end effector will result in significant increases in the subject's quality of life	Quality of Life Inventory (QOLI) administered by the NPS operator	During prescreening (baseline) and every month subsequent to implantation	Monthly QOLI score will be compared against baseline

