Key Inclusion Criteria	Paralysis (high cervical spinal lesion, C4 or above) initiated at least one year prior and stable for at least 3 months prior.
Key Exclusion Criteria	Active psychiatric or medical illness which precludes surgery, stable participation in study sessions, or which requires MRI or other contraindicated procedure during time enrolled.
Primary Efficacy Objective, Analysis, and Methods	The primary effectiveness objective is to evaluate the long-term effectiveness of the NPS. The primary outcome variable is the accuracy with which tasks are performed during study sessions, which will be compared to the level of chance. The secondary outcome variable is scoring on the Action Research Arm Test, a standard test used in occupational therapy to measure upper extremity limb function following cortical damage. The tertiary outcome variable is the quality-of-life index, measured before and after the study.
Primary Safety Objective, Analysis, and Methods	The primary safety objective is to evaluate the safety of the NPS. The primary outcome variable is the presence of infection or irritation around the implant site. The secondary outcome variable is the Severe Adverse Event (SAE) rate measured per subject as a percentage of implant-days. These factors will be measured during clinical follow-up care using standard observations and exams.

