### 1.5 Central Hypotheses

We hypothesize the following regarding the safety of the device:

- (1) Implantation will not be associated with infection or irritation;
- (2) The Severe Adverse Event (SAE) rate, calculated as the number of SAEs per implant-day, will not rise above 1% for any study subjects.

We hypothesize the following regarding the effectiveness of the device:

- (1) Control over virtual and physical end effectors, as measured by accuracy, will be significantly greater than chance when using the NPS;
- (2) Action Research Arm Test (ARAT) scores will improve over the course of the trial when controlling virtual or physical end effectors
- (3) Using the NPS with either virtual or physical end effectors will result in significant increases in the subjects' quality of life.

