## 2.0 Objectives and Purpose

### 2.1 Primary Safety Objective

The primary objective of this study is to evaluate the safety of the NPS. The driving hypotheses are that the implantation will not be associated with infection or irritation, and that the SAE rate will not rise above 1%. These hypotheses will be evaluated via the endpoints defined in Section 10.1.

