### 10.1.2 SAE Rate

The severe adverse event (SAE) rate is the secondary safety endpoint. The indicated SAE rate threshold, at 1% SAEs per implant-days, was established based on literature describing adverse events for similar procedures (107, 108).

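### Comparing the running SAE rate continuously with 1% lets timing largely decide the verdict on a few SAEs: on the natural reading, a single SAE breaches on implant-days 1 to 99 and never from day 100

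*Protocol*

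**What the plan says.** The Protocol's Study Synopsis introduces the endpoint: "The secondary outcome variable is the Severe Adverse Event (SAE) rate measured per subject as a percentage of implant-days". Section 1.5 states the hypothesis, with the rate "calculated as the number of SAEs per implant-day, will not rise above 1% for any study subjects". Section 2.1 repeats the 1% limit.

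Table 10-1 in section 10.0 supplies the operating rule. On timing: "The SAE rate will be available on a daily basis throughout the study". On the comparison: "The SAE rate will be continuously compared to the 1% threshold level".

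Section 10.1.2 gives the origin of the limit: "The indicated SAE rate threshold, at 1% SAEs per implant-days, was established based on literature describing adverse events for similar procedures". It shows no derivation.

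The endpoint counts *severe* adverse events, but section 8.2.1 has a definition only for those called *serious*: "Any adverse event that results in any of the following outcomes: death, a life-threatening adverse effect, inpatient hospitalization or prolongation of existing hospitalization", among other outcomes.

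Neither document says which implant-days form the denominator on a given day, whether a temporary crossing counts against the hypothesis, or on what date the verdict is taken. The SAP (sections 13.1 to 13.5) does not mention the SAE rate.

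**The concern.** Early in follow-up the denominator of a running ratio is small, so one event makes the ratio large. As days accrue without a further event, the ratio falls by itself. Set against a fixed 1% every day, the same single SAE fails the hypothesis if it comes in the first 99 days and passes if it comes later. Surgery and healing also lie at the start, where the rule is strictest.

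The report could therefore say that a subject's SAE rate rose above 1% when that subject's rate over the full implant was 0.27%. Protocol section 13.4 says that the outcomes in these two subjects will inform whether more and larger studies are warranted, and this verdict is one of those outcomes.

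**Working it through.** **Inputs from the Protocol.** Threshold 1%, breached only if the rate is above it (1.5, Table 10-1). Rate = SAEs divided by implant-days, per subject (Synopsis, Table 10-1). Two subjects, 53 weeks implanted (3.1): 53 × 7 = 371 days. Tables 3-1 and 18-1 place explantation 52 weeks after implantation: 52 × 7 = 364 days. The 1% figure cannot be reproduced, because no derivation is given.

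**Assumptions.** The denominator is implant-days to date, the day of implantation is day 1, and any crossing counts as having risen above 1%. The documents give no expected SAE rate, so a range of constant daily probabilities p is used.

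**Step 1: when a given count breaches.** After k SAEs on day d the ratio is k/d, and k/d > 0.01 exactly when d < 100k.
- One SAE: 1/99 = 1.01% (above); 1/100 = 1.00% (not above). Breach days are 1 to 99, which is 99/371 = 26.7% of the implant period.
- The second SAE breaches only before day 200 and the third only before day 300. A fourth breaches on any day up to 371.

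**Step 2: the ratio at the end of a full implant.**

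| SAEs | 371 days | 364 days |
|---|---|---|
| 1 | 0.27% | 0.27% |
| 2 | 0.54% | 0.55% |
| 3 | 0.81% | 0.82% |
| 4 | 1.08% | 1.10% |

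One to three SAEs always finish below 1%. If they fall on distinct random days of 371, they also avoid a breach on the way in 73%, 46% and 19.5% of cases. For one SAE this is 272/371 = 73%.

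**Step 3: probability of a breach with full 371-day follow-up.** Continuous rule: day-by-day recursion, breach on the first day with 100k > d. Single evaluation: P(X ≥ 4) with X ~ Binomial(371, p). For two subjects: 1 − (1 − q)², where q is the per-subject probability.

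| p per day | Continuous, per subject | Continuous, at least one of two | Judged once at day 371, per subject |
|---|---|---|---|
| 0.01% | 1.0% | 2.0% | below 0.001% |
| 0.1% | 9.9% | 18.8% | 0.06% |
| 1% | 79% | 96% | 51% |

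**Step 4: explantation at the first SAE.** The final ratio then equals the running ratio on the day of the SAE, so both rules breach exactly when the SAE falls on days 1 to 99. At p = 0.1% per day: 1 − 0.999^99 = 9.4% under either rule. This case matters because section 5.3 lists "Development of serious adverse events, physical or psychological" as a withdrawal criterion, and section 8.2.9 makes explantation before withdrawal the default.

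**Step 5: what an interval would show.** Exact Poisson 95% limits for the count are 0 to 3.689 for no events and 0.0253 to 5.572 for one.
- No SAE: upper limit 3.689/371 = 0.99% per day, or 3.689/364 = 1.01%.
- One SAE over 371 days: 0.007% to 1.50% per day.
- One SAE with explantation on day 10: 10% per day, interval 0.25% to 56%.

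**The case against.** **The consequence is small.** This is a secondary endpoint in two subjects. No action is tied to crossing 1%, SAEs are handled one by one (5.3, 8.2.6, 8.2.7, 8.2.9), and section 13.4 disclaims power for conclusions on absolute safety. Anyone planning the next study will see each SAE. All of this stands and sets the limit of the point.

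**The rule does follow the rate.** A reader might infer that the verdict says nothing about the SAE rate. That goes too far: breach probability rises from 1.0% to 9.9% to 79% as the assumed rate goes from 0.01% to 0.1% to 1% per day. The running ratio is noisy early, but it is not uninformative.

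**The 9.9% against 0.06% contrast needs full follow-up.** This stands. A reader might infer that judging once at the end solves the problem. Step 4 shows otherwise: when the SAE ends the implant, the two rules agree.

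**Early sensitivity could be a deliberate monitoring flag.** No section says so. A list of SAEs by implant-day would keep early events just as visible.

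**The text could be clarified and the verdict kept.** Stating the denominator, the evaluation date and the treatment of crossings would remove the ambiguity. It would not remove the dependence on timing if crossings count, nor after early explantation if only the final ratio counts. The proposed rate also depends on timing after early explantation (10% per day in the day-10 example), but its interval shows how little that figure says.

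**Conclusion.** The point holds under the stated reading: implant-days to date, with any crossing counting. On that reading the verdict on one to three SAEs is driven largely by when they occur, and for one SAE entirely so. It is a poor summary of a subject's SAE rate. With full follow-up at an assumed 0.1% per day, 9.9% of subjects breach under the continuous rule against 0.06% judged once. With explantation at the first SAE the figure is about 9.4% under both.

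The reading is the natural one for a rate that is available daily and compared continuously, but the documents do not state it. Other counting conventions could move the day-99 cut. Nor do the documents support the inference that a crossing would stop the study or change a subject's care. The damage is limited to what is reported for this endpoint. It is worth correcting because the change needs only wording.

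**What to change.** 1. In Table 10-1, and consistently in sections 1.5, 2.1 and 10.1.2, stop using the continuous comparison with 1% as a pass/fail verdict. Any daily running ratio may stay as a description, with its denominator stated as implant-days to date.
2. For every subject, including those explanted early, report the SAE count, implant-days, rate and exact Poisson 95% interval at explantation or at the end of the 53 weeks, whichever comes first. Label the interval approximate when the SAE itself ends exposure. Show 1% per implant-day as a reference value only.
3. List each SAE with its implant-day.
4. Report separately any time with a device retained beyond the study period (3.1, 5.3).
5. Name the numerator by the term defined in section 8.2.1, serious adverse event, in the Synopsis, 1.5, Table 10-1 and 10.1.2. The Synopsis contains no 1% comparison and needs only this terminology change.

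**Cost.** Wording only; no extra data and no change to clinical management. The endpoint becomes descriptive and the intervals are wide. Even with no SAEs the upper limit is 0.99% per day over 371 days and 1.01% over 364, so a firm claim that a subject's rate is below 1% would not be available.
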